2. RATIONALE, OBJECTIVES, AND BENEFIT - RISK ASSESSMENT

2.1 RATIONALE FOR PERFORMING THE TRIAL

Although considerable progress has been made in understanding tumour biology as well as in developing more effective treatment regimens, most patients with locally advanced or metastatic tumours will succumb to their disease. Thus, there is a substantial need for novel therapeutic strategies to improve the outcome for patients with advanced or metastatic malignancies for whom conventional treatment has failed, or for whom no therapy of proven efficacy exists.

Cell-cycle targeted therapies represent a novel and promising approach in these patients ([R04-0415](#)). Mitotic kinases regulating cell division and its checkpoints are considered particularly attractive targets for new therapies ([R04-0421](#)). Volasertib represents a new class of small molecules targeting and blocking activation of PLK with high selectivity and specificity. This compound induces cell cycle arrest, apoptosis and tumour shrinkage at tolerable doses in preclinical tumour models. In the clinical setting antitumour activity was reported in phase I and phase II trials (see IB).

This open label phase I trial 1230.24 will investigate the influence of co-administration of volasertib and itraconazole, a potent inhibitor of P-gp and cytochrome P450 3A4 in comparison to administration of volasertib without influencing itraconazole.

In vitro tests have shown that volasertib is a substrate of cytochrome P450 3A4 as well as a highly potent inhibitor of P-gp ([U08-2116](#), [U08-3450](#)).

Volasertib distributes rapidly into a large volume (>4000 liters). The current PK data suggest that the terminal elimination half-life represents rather the slow re-distribution of Volasertib from deeper compartments into the blood stream than the elimination from the systemic circulation. Since that Volasertib is a P-gp substrate the distribution might be influenced by P-gp inhibitors.

Male and female patients with various solid tumours for whom conventional treatment has failed, or for whom no therapy of proven efficacy exists, or who are not amenable to established forms of treatment will be treated with volasertib in this study. Volasertib will be given as a single infusion over 120 minutes on day one of the study. Based on the safety profile from study 1230.1, the first in man trial of volasertib, the recommended phase II dose of 300 mg will be given.

Determination and quantification of the influence of co-administration of itraconazole and volasertib compared to volasertib without influencing factors is the primary endpoint of this trial. This effect will be evaluated in the first two treatment cycles.

If clinical benefit from volasertib treatment is indicated, patients may receive additional cycles of volasertib. In these additional cycles no drug-drug interaction will be evaluated. Patients who experience a clinical benefit, i.e. an objective tumour response or symptom

Proprietary confidential information.

© 2017 Boehringer Ingelheim International GmbH or one or more of its affiliated companies. All rights reserved.
This document may not - in full or in part - be passed on, reproduced, published or otherwise used without prior written permission.

improvement or the absence of tumour progression and who have recovered from drug-related adverse events from previous cycles are eligible for additional cycles of volasertib according to protocol.

Secondary endpoints of this trial are safety, tolerability and the assessment of preliminary therapeutic effects of volasertib.

2.2 TRIAL OBJECTIVES

The primary objective of the present study is to investigate the influence of co-administration of itraconazole (a potent dual inhibitor of cytochrome P450 3A4 and P-gp) and volasertib on the pharmacokinetic profile of volasertib without co-administration of itraconazole. Secondary objectives are to investigate safety, tolerability and preliminary therapeutic effects following intravenous administration of volasertib.

2.3 BENEFIT - RISK ASSESSMENT

The most relevant side effect of volasertib administration is expected to be a transient inhibition of proliferation of normal dividing cells in bone marrow and mucosal tissue. The side effects on bone marrow stem cells lead to a temporary decrease in the number of blood cells and platelets (reversible events of neutropenia, febrile neutropenia, thrombocytopenia and anaemia), as reported by the DLTs and adverse events in clinical trials. . Transient inhibition of haematopoiesis may be followed by clinical symptoms and complications as e.g. infections in neutropenic patients, bleedings in thrombocytopenic patients and fatigue in anaemic patients; respective drug related adverse event were reported in the clinical trials with volasertib. The majority of adverse events of CTCAE grade 3 or higher reported in clinical trials and considered related to volasertib are decrease of blood cells (anaemia, neutropenia and thrombocytopenia) and associated complications. Inhibition of mucosal proliferation may lead to gastrointestinal symptoms such as nausea or diarrhoea, although this finding was reported only in a limited number of patients so far. Other frequently reported adverse events were reported mostly with mild to moderate severity (nausea, decreased appetite, vomiting, constipation, alopecia).. These side effects are frequently seen in tumour patients treated with conventional cytotoxics or kinase inhibitors and can easily be monitored. Supportive treatment for these effects is available.

QT prolongation was seen in preclinical models. QTcF prolongations in the 20-30ms range at C_{max} were observed in the first phase I trial without occurrence of relevant clinical events. This observation will be further characterized by ECG monitoring in the phase I and II program. Mild to moderate cardiac lesions were seen in chronically treated dogs. Given that no cardiac events were reported in patients but clinical benefit was already observed in a heavily pre-treated Phase I patient population a positive risk-benefit ratio was concluded. Nevertheless, biomarkers for cardiotoxicity (Troponin, CK) and ECGs including QTc assessment will remain a part of the clinical safety monitoring in any phase I/II study.

Proprietary confidential information.

© 2017 Boehringer Ingelheim International GmbH or one or more of its affiliated companies. All rights reserved.
This document may not - in full or in part - be passed on, reproduced, published or otherwise used without prior written permission.

Cancer patients with advanced tumours and no further treatment options may benefit from tumour shrinkage, tumour stabilization or improvement of tumour-related symptoms as a result of treatment with volasertib. The potential benefit of therapy with volasertib is expected to outweigh the treatment related risks.

Restrictions for CYP3A4/Pgp inhibitors/inductors are only relevant for the drug-drug interaction part of the study, as these drugs may potentially interfere with the metabolism and distribution of volasertib. For the non-drug-drug interaction part other cytotoxic and anticancer immunotherapies are not allowed while CYP3A4/Pgp inhibitors/inductors are allowed.

Although rare, a potential for drug-induced liver injury (DILI) is under constant surveillance by sponsors and regulators. Therefore, this study requires timely detection, evaluation and follow-up of laboratory alterations of selected liver laboratory parameters to ensure patients' safety.

Proprietary confidential information.

© 2017 Boehringer Ingelheim International GmbH or one or more of its affiliated companies. All rights reserved.
This document may not - in full or in part - be passed on, reproduced, published or otherwise used without prior written permission.

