4.1.3.1 Potential dose reduction

Reduction of starting dose

Initially, patients will be treated sequentially. Single patients will be treated for the first cycle until three patients have completed the first cycle.

Thereafter, cohorts of 3 patients will be treated until the preliminary safety of volasertib in combination with itraconazole is confirmed.

If more than 1 out of 6 patients experiences unacceptable toxicity (DRT, Section 5.2.6) during the first treatment cycle, the dose of volasertib for subsequent patients will be deescalated to 250 mg in the first and second treatment period.

If more than 1 out of 6 patients treated at a volasertib dose of 250 mg experiences unacceptable toxicity during the first treatment cycle, the dose of volasertib for subsequent patients will be further deescalated to 200 mg in the first and second treatment period.

The highest dose for which the incidence of unacceptable toxicity is no more than 1 out of 6 will be used as the dose of volasertib for the first and second treatment cycle of all further patients included in the trial (MTD, cf. [Section 5.2.6](#)).

Dose reduction in individual patients

If a patient experiences unacceptable toxicity (DRT, Section 5.2.6) the patient can continue volasertib treatment at a lower dose if criteria for retreatment are met (see [Section 3.3.5](#)). Each occurrence of DRT will lead to a dose reduction by 50 mg of any subsequent volasertib infusion(s). No dose reduction of volasertib below 200 mg is allowed.

If a patient experiences a DRT at the 200 mg dose, i.e. a dose reduction to <200 mg would be required, the volasertib treatment will be permanently discontinued and the patient will move to the EoT visit.

Proprietary confidential information.

© 2017 Boehringer Ingelheim International GmbH or one or more of its affiliated companies. All rights reserved.
This document may not - in full or in part - be passed on, reproduced, published or otherwise used without prior written permission.

When a dose reduction of volasertib occurs, this applies to all subsequent cycles with no possibility to dose escalation back to the previous dose.

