4.1.3.2 Dose escalation scheme

A patient who is eligible to continue therapy with volasertib beyond the 2nd cycle (see [Section 3.3.5](#)) may either be treated with the original dose or may receive a higher dose in the third and subsequent cycles. The dose can be increased by 50 mg after each cycle ≥ 2 up to a maximum dose of 350 mg in case of clinical benefit and good tolerability in the completed cycle (i.e., non-hematological drug related adverse events of less than CTCAE Grade 2 and / or hematological drug related adverse events of less than CTCAE Grade 3). Dose escalation will occur only upon agreement between investigator and sponsor. Patients should continue on the higher dose in all subsequent treatment cycles if well tolerated. The decision to escalate the dose can be made at the end of cycles ≥ 2 . No dose increases above 350 mg are allowed. After dose escalation to the 350 mg subsequent dose reductions are allowed as per [Section 4.1.3.1](#).

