4.2.2 Restrictions

4.2.2.1 Restrictions regarding concomitant treatment

Additional chemo-, immuno-, hormone, radio-, or molecular-targeted cancer-therapy is not permitted during the study. These restrictions do not apply to steroids and bisphosphonates as well as to hormonal / antihormonal treatment e.g. in prostate or breast cancer. For symptom control, palliative radiotherapy may be permitted after discussion with the BI Clinical Monitor.

The following potent CYP 3A4 and P-glycoprotein inhibitors or inducers are not permitted from one week prior to first drug administration until the last PK sample is collected:

Strong CYP 3A4 inhibitors: atazanavir, clarithromycin, indinavir, ketoconazole, itraconazole, nefazodone, neflavinavir, ritonavir, saquinavir, telithromycin

CYP 3A4 inducers: carbamazepine, rifampicin

P-gp inhibitors: cyclosporine, erythromycin, ketoconazole, itraconazole, quinidine, phenobarbital salt with quinidine, ritonavir, valspodar, verapamil

P-gp inducers: hypericum perforatum (St. John's wort), rifampicin

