5.5.1 Pharmacokinetic endpoint(s)

Pharmacokinetic parameters will be evaluated by means of noncompartmental analysis. The derivation of pharmacokinetic parameters is described in detail in the internal SOP 001-MCS-36-472_RD-01.

Primary endpoints (volasertib and CD 10899):

[figure not shown]
- maximum measured plasma concentration (C_{max})
- area under the plasma concentration-time curve over the time interval from zero to the last quantifiable drug plasma concentration after dose administration (AUC_{0-tz})

Secondary endpoint (volasertib and CD 10899):

- area under the plasma concentration-time curve over the time interval from zero extrapolated to infinity ($AUC_{0-\infty}$)

Proprietary confidential information.

© 2017 Boehringer Ingelheim International GmbH or one or more of its affiliated companies. All rights reserved.
This document may not - in full or in part - be passed on, reproduced, published or otherwise used without prior written permission.

All pharmacokinetic measurements will be performed only in first two treatment cycles.

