6. INVESTIGATIONAL PLAN

6.1 VISIT SCHEDULE

The patients will stay at the investigator site from the evening before first itraconazole administration (day -4) until day 4 of the first cycle as well as from the day before intravenous infusion of volasertib until 72 hours after start of infusion of the second cycle (day -1 until day 4). Ambulatory visits will happen 168 hours (day 8), 336 hours (day 15) and 504 hours (day 22) after start of infusion, where the last visit may coincide with day 1 of consecutive treatment cycles. In this case the blood sample for PK has to be taken before administration of the study drug.

Procedures will be performed as outlined in the [flow chart](#). In third and subsequent treatment cycles the patient will visit the investigator at regular intervals as specified in the flow chart (visit 2 and 3 are optional visits at the investigator's discretion) for determination of safety laboratory parameters, recording of adverse events and additional procedures as outlined in the flow chart. If a patient misses a visit and the patient reports to the investigator between this and the next scheduled visit, the missed visit should be performed with the actual date and the reason should be given for the delayed visit. The next visit, however, should take place as scheduled relative to the first administration of the trial drug in the treatment cycle.

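### From cycle 3 itraconazole and other CYP3A4/P-gp inhibitors are allowed with no volasertib dose limit, so a compliant patient can be dosed at 1.2 or 1.4 times the trial's own 250 mg combination MTD

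*Protocol*

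**What the plan says.** **Inhibitors.** Protocol 2.3 confines the CYP3A4/P-gp restriction to the interaction part, because these drugs may interfere with volasertib metabolism and distribution. It then continues: "For the non-drug-drug interaction part other cytotoxic and anticancer immunotherapies are not allowed while CYP3A4/Pgp inhibitors/inductors are allowed". Section 4.2.2.1 lists the drugs, itraconazole among them, as "not permitted from one week prior to first drug administration until the last PK sample is collected". Section 5.5.1 fixes when that is: "All pharmacokinetic measurements will be performed only in first two treatment cycles". The day 22 visit of cycle 2 may coincide with day 1 of cycle 3, and section 6.1 adds: "In this case the blood sample for PK has to be taken before administration of the study drug".

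**Dose.** Section 4.1.3.2 allows 50 mg increases after each cycle from cycle 2 onward, "up to a maximum dose of 350 mg in case of clinical benefit and good tolerability". It also says: "Dose escalation will occur only upon agreement between investigator and sponsor".

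**Combination MTD.** Section 5.2.6 defines the MTD for volasertib given with itraconazole. Under 4.1.3.1 the dose that meets the definition "will be used as the dose of volasertib for the first and second treatment cycle of all further patients included in the trial". SAP 4 and 7.4 report that three patients were treated at 300 mg with itraconazole, that two of them stopped after cycle 1, that the MTD was then lowered to 250 mg, and that all later patients were treated at 250 mg. One patient had 300 mg in both cycles.

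**The concern.** The trial learned that 300 mg with itraconazole was too much as a starting dose and moved to 250 mg. That finding governs cycles 1 and 2 only. From cycle 3 the protocol opens two doors independently: the inhibitor may return, and the volasertib dose may rise. Nothing stops both from happening in the same patient at the same infusion.

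The reason given in 2.3 for the restriction, interference with how volasertib is metabolised and distributed, does not stop when PK sampling stops. The main toxicity is bone-marrow suppression, and Protocol 1.2 describes potentially dose-dependent QTcF prolongation around Cmax. What is at stake is the safety of the patients who continue, not the interaction estimate.

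**Working it through.** The plan states no figure on this point, so there is nothing to reproduce. The check is a reading of the rules together with simple dose ratios.

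**1. When the inhibitor ban ends.** Sections 4.2.2.1 and 5.5.1 put the end at the last cycle 2 sample, 504 h (day 22). When that visit is also day 1 of cycle 3, the sample comes before the infusion (6.1). The ban can therefore be over before the cycle 3 dose is given.

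**2. Who can be escalated.** Section 4.1.3.1 says of an individual reduction that "this applies to all subsequent cycles with no possibility to dose escalation back to the previous dose". That blocks a patient reduced from 250 to 200 mg. It does not block a patient whose starting dose was 250 mg, because that patient has had no individual reduction.

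**3. Dose path.** Inputs: 50 mg per step and a 350 mg ceiling (Protocol 4.1.3.2); combination MTD 250 mg (SAP 4). Ratio = dose / 250.

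| Cycle 2 dose | Cycle 3, at most | Cycle 4, at most |
|---|---|---|
| 250 mg | 300 mg: 300/250 = 1.2 | 350 mg: 350/250 = 1.4 |
| 300 mg (one patient, already at 1.2) | 350 mg: 1.4 | 350 mg: 1.4 |
| 200 mg after reduction | 200 mg: 200/250 = 0.8 | 200 mg: 0.8 |

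**4. Is dose linked to inhibitor use anywhere?**

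- 4.1.3.2 asks for clinical benefit, good tolerability in the completed cycle and joint agreement. For the first escalation the completed cycle is cycle 2, when listed inhibitors are banned. An inhibitor may also be started after an escalation.
- 3.3.5 asks for benefit, neutrophil and platelet thresholds, and recovery from toxicity.
- 4.1.3.1 and 5.2.6 lower the dose after a dose-reducing toxicity (DRT).
- 5.2.4 looks at concomitant medication when QTcF is prolonged, for example when a pre-infusion value above 470 ms withholds the drug.

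None of these sets a volasertib dose because an inhibitor is present.

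**5. How many drugs are released.** Section 4.2.2.1 lists 10 strong CYP3A4 inhibitors and 9 P-gp inhibitors. Three (itraconazole, ketoconazole, ritonavir) are on both lists. That makes 10 + 9 - 3 = 16 drugs. The trial's combination MTD concerns one of them, itraconazole; for the other 15 the documents give no combination dose.

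**The case against.** The permission is open and sits inside the benefit-risk section, so it is a disclosed choice. A reader might infer that the protocol contradicts its own MTD. It does not: 4.1.3.1 limits the MTD to the first two cycles, and no rule is broken.

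The controls are real. Every continuing patient has already had volasertib with itraconazole. Each escalation needs the sponsor's agreement, and concomitant drugs are recorded, so the information is available when the decision is made. Retreatment still requires blood counts, and ECGs before and at the end of each infusion continue after revision 3. Grade 4 neutropenia requires a further sample within seven days. This makes the risk small. It does not close the gap: apart from the first three patients, the cycle 1 experience was at 250 mg, and the checks either precede the infusion or respond to toxicity. Day 8 and day 15 visits in later cycles are optional, and laboratory tests have been largely discretionary since revision 3.

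It can also be said that 350 mg lies below the single-agent MTD of 400 mg (Protocol 1.2). That is true of volasertib alone. How much of the margin an inhibitor uses up depends on an interaction ratio that the documents do not give.

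Finally, the 250 mg figure comes from 18 daily doses of itraconazole, from three days before the infusion to day 15. An inhibitor first taken on the infusion day is a different exposure, and other drugs are different again. This stands, and it is why a firm 250 mg cap should not be extended beyond itraconazole.

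**Conclusion.** The concern holds as a missing dose condition: a compliant patient may receive itraconazole with 300 or 350 mg volasertib, 1.2 or 1.4 times the combination MTD. It rests on the SAP's record of a 250 mg MTD and on reading 2.3 and 4.2.2.1 as releasing itraconazole with the other listed drugs.

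Three stronger readings are not supported.

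- **Excess exposure or risk of 20% or 40%.** The ratios compare doses. The interaction size is not stated, and SAP 7.4 says proportionality was not established under itraconazole.
- **A known toxicity rate at 300 mg.** The SAP reports two of three patients stopping after cycle 1, not how many had a DRT. No rate can be computed.
- **Invalid safety tables.** SAP 6.1 defines the mono-therapy period by volasertib dates alone, so inhibitor cycles are not marked in the summaries. But medications are recorded and listed (Protocol 4.2, SAP 7.2) and can be traced. Cycle 2 lies within the ban, so the cycle 1 versus cycle 2 contrast is unaffected.

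The number of patients concerned is unknown and probably small. The primary PK analysis uses cycles 1 and 2 only and does not change.

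**What to change.** Add to Protocol 4.1.3.2 and 4.2.2.1, with a cross-reference in 2.3:

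- *From cycle 3, a patient taking itraconazole at an infusion or in the week before it receives no more than 250 mg volasertib, or the patient's own lower dose, and is not escalated in that cycle. A patient who has already tolerated 300 mg with itraconazole without a DRT may stay at 300 mg after documented investigator-sponsor review.*
- *For any other CYP3A4 or P-gp inhibitor listed in 4.2.2.1, use is checked before each infusion, and there is no escalation above 250 mg without documented investigator-sponsor review.*

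The lighter second rule reflects the absence of data on those drugs. With the first rule the itraconazole ratio is at most 250/250 = 1.0, or 300/250 = 1.2 under the reviewed exception. A dose rule cannot cover an inhibitor started after the infusion.

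Optional, in SAP 6.1 and 7.8.1: flag cycles with a listed inhibitor in use at infusion in the mono-therapy safety listings, from medication dates already in the eCRF. Keep every cycle in the main tables. The list includes anti-infectives and infection is a known volasertib complication, so dropping cycles in which such a drug was started after dosing would remove toxicity.

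**Cost.** A lower dose for the few patients affected, and a protocol amendment that needs ethics and authority approval before use (Protocol 8.1). The benefit is limited to patients still on treatment, because by revision 3 the programme had been discontinued.

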3. DESCRIPTION OF DESIGN AND TRIAL POPULATION

3.1 OVERALL TRIAL DESIGN AND PLAN

This trial is an uncontrolled, open-label, sequential drug-drug interaction study of volasertib and itraconazole in tumour patients. Patients with advanced, non-resectable and/or metastatic solid tumours will be eligible for the study if conventional treatment has failed or if they are not amenable to established treatment options. Patients will be assessed for eligibility at a screening visit within 14 days prior to first drug administration. For the first treatment cycle patients will receive 200 mg of itraconazole starting 3 days before the first intravenous infusion of volasertib. On day 1 patients will receive an intravenous infusion with volasertib, whilst itraconazole dosing continues for 14 days/until 336 hours after volasertib infusion. PK samples will be taken until 504 hours after start of infusion.

After this 504 hours blood sample has been withdrawn and if none of the criteria for removal of patients from therapy or assessments is met (see [section 3.3.4](#)), patients will receive a second infusion of volasertib with clinical activities as outlined in the flow chart for treatment cycle 2. This cycle will be identical to the first cycle with the exception that no administration of itraconazole occurs in cycle 2.

The patients will be admitted to hospital for the time period of itraconazole administration from 88 hours before until 72 hours after start of infusion of volasertib in cycle 1 and the night before until 72 hours after start of infusion in treatment cycle 2, subsequent treatment cycles can be administered on an outpatient basis at the discretion of the investigator. The patients will visit the investigator at regular intervals as specified in the [flow chart](#) for determination of safety laboratory parameters, recording of adverse events and additional investigations as outlined in the [flow chart](#). A radiological assessment of tumour response will be performed at discretion of the investigator.

Initially, patients will be treated sequentially. Single patient cohorts will be treated for the first cycle until three patients have completed the first cycle.

Thereafter, cohorts of 3 patients will be treated until the preliminary safety of volasertib in combination with itraconazole is confirmed (for details see [section 4.1.3.1](#)).

After implementation of Protocol revision 3, safety laboratory parameters and additional investigations (weight, ECOG, vital signs, physical examination etc) as outlined in the Flow chart will be done as medically indicated at discretion of the investigator. Investigator will continue recording ECG prior and at the end of volasertib infusion to ensure patient safety. For this purpose investigator will use local ECG machine, centralized ECG analysis will be discontinued.

Clinical response assessment after every cycle and radiological assessment at the investigator's discretion will be continued to support the investigator's decision on treatment continuation/discontinuation.

